5.2. Exclusion Criteria

Participants are excluded from the study if any of the following criteria apply:

Medical Conditions

1. Participant has a Screening alanine transaminase (ALT) value of > 2.0 x upper limit of normal (ULN);

- 2. Participant has a Screening total bilirubin value of $> 1.5 \times ULN$ (isolated bilirubin $> 1.5 \times ULN$ is acceptable if bilirubin is fractionated and direct bilirubin < 35%);
- 3. Participant has a history of malignancy associated hypercalcemia;
- 4. Participant has an active parathyroid disorder, hyperphosphatemia at Screening (serum phosphorus > 1 x ULN), or serum calcium (mg/dL) x serum phosphorus (mg/dL) product > 70 at Screening;
- 5. Any clinically significant active or known history of liver disease, or known hepatic or biliary abnormalities (with the exception of Gilbert's syndrome or asymptomatic gallstones);
 - 5.1. Hepatitis serology and viral load will be tested at Screening. Patients who are hepatitis B surface antigen (HBsAg) positive or hepatitis C virus (HCV) antibody positive at Screening must not be enrolled until further definite testing with hepatitis B virus (HBV) deoxyribonucleic acid (DNA) titers is < 500 IU/mL or HCV ribonucleic acid (RNA) polymerase chain reaction test is negative;
- 6. Lymphoma, leukemia, or any malignancy (including malignant glioma or MPNST) within the past 5 years except for basal cell or squamous epithelial carcinomas of the skin that have been resected with no evidence of metastatic disease for 3 years;
- 7. Breast cancer within the past 10 years;
- 8. Participants with evidence of an active optic glioma or other low-grade glioma, requiring treatment with chemotherapy or radiation therapy. Participants not requiring treatment are eligible. Ophthalmological findings secondary to long-standing optic pathway glioma (such as visual loss, optic nerve pallor or strabismus) or long-standing orbito-temporal PN (such as visual loss, strabismus) will NOT be considered a significant abnormality for the purposes of the study;
- 9. Participant has abnormal QT interval corrected by Fridericia's formula (> 450 msec for male participants, > 470 msec for female participants, or > 480 msec for participants with bundle branch block) (triplicate ECG readings taken approximately 2 to 3 minutes apart and averaged) at Screening;
- 10. Participant has experienced any of the following within 6 months (24 weeks) of signing informed consent/assent: clinically significant cardiac disease, myocardial infarction, severe/unstable angina, coronary/peripheral artery bypass graft, cerebrovascular accident, transient ischemic attack, or symptomatic pulmonary embolism;
- 11. Participant has recorded a LVEF < 55% at Screening or within 3 years of signing informed consent/assent, OR has a history of congestive heart failure;
- 12. Participant has a history of, or evidence of, retinal pathology on ophthalmologic examination that is considered a risk factor for central serous retinopathy, retinal vein occlusion (RVO), or neovascular macular degeneration. Participants will be excluded from study participation if they have any of the following risk factors for RVO at Screening:

- 12.1. Intraocular pressure > 21 mmHg;
- 12.2. Serum cholesterol > 300 mg/dL;
- 12.3. Serum triglycerides > 300 mg/dL;
- 12.4. Hyperglycemia (fasting blood glucose > 125 mg/dL or random blood glucose > 200 mg/dL);
- 12.5. Age specific hypertension
 - 12.5.1. Participants \geq 13 years of age with a blood pressure \geq 140/90 mm Hg
 - 12.5.2. Participants \leq 12 years of age with a blood pressure \geq 95th percentile for age +12 mmHg (Section 10.11);
- 13. Participant has a history of glaucoma;
- 14. Participant has a history of a positive human immunodeficiency virus (HIV) antibody test;
- 15. Participant has a known malabsorption syndrome or preexisting gastrointestinal conditions that may impair absorption of PD-0325901 (e.g., gastric bypass, lap band, or other gastric procedures). Delivery of PD-0325901 via nasogastric tube or gastrostomy tube is not allowed;

Prior/Concomitant Therapy

- 16. Participant has received NF1 PN-targeted therapy (e.g., farnesyltransferase inhibitors, kinase inhibitors, etc.) within 45 days of first dose of study treatment (or 5.5 half-lives, whichever is longer). All toxicities from prior therapy must resolve to ≤ Grade 1 or Baseline;
- 17. Participant previously received or is currently receiving therapy with PD-0325901 or any other MEK1/2 inhibitor (e.g., selumetinib, trametinib, cobimetinib, binimetinib, etc.);
- 18. Participant is receiving systemic, inhaled, or ocular glucocorticoid therapy (with the exception of participants with endocrine deficiencies who are allowed to receive physiologic or stress doses of steroids, if necessary) within 14 days prior to first dose of study treatment;
- 19. Participant has received radiation therapy within the 6 months prior to signing of informed consent/assent. Participants who have received radiation to the orbit at any time are excluded;

Prior/Concurrent Clinical Study Experience

20. Current enrollment or past participation in any other clinical study (excluding observational studies) within 28 days of signing of informed consent/assent;

Other Exclusions

- 21. Participant is unable to tolerate MRI or for whom MRI is contraindicated;
- 22. Tumor is not able to be reliably evaluated by MRI volumetric analysis;

- 23. Sensitivity to the study treatment, or components thereof, or drug or other allergy that, in the opinion of the Investigator or Medical Monitor, contraindicates participation in the study;
- 24. Participant with active bacterial, fungal, or viral infection including but not limited to the use of antibiotics, antifungals, or antiviral agents at the time of Screening;
- 25. Underlying medical conditions, laboratory abnormality, or alcohol or drug abuse or dependence that, in the Investigator's opinion, will be unfavorable for the administration of study treatment or affect the explanation of drug toxicity or adverse events; or insufficient compliance during the study according to Investigator's judgement; or
- 26. Participant has experienced other severe acute or chronic medical or psychiatric conditions, including recent (within 1 year of signing informed consent/assent) or active suicidal ideation or behavior, or a laboratory abnormality that may increase the risk associated with study participation or study treatment administration or may interfere with the interpretation of study results and, in the judgment of the Investigator, would make the participant inappropriate for entry into this study.

5.3. Lifestyle Considerations

- 1. There are no lifestyle restrictions in this study.
- 2. Study treatment may be taken without regard to food.
- 3. Refer to Section 6.5 for more detail on concomitant therapy including exclusions and restrictions.

5.4. Screen Failures

Screen failures are defined as participants who consent/assent to participate in the clinical study but are not subsequently assigned to study treatment (PD-0325901) at Cycle 1 Day 1 of the Treatment Phase. A minimal set of screen failure information is required to ensure transparent reporting of screen failure participants to meet the Consolidated Standards of Reporting Trials publishing requirements and to respond to queries from regulatory authorities. Minimal information includes demography, screen failure details, eligibility criteria, and any serious adverse event (SAE).

Individuals who do not meet the criteria for participation in this study (screen failure) may be rescreened at any time and do not need to wait the full 45 days of the Screening period. These cases must be discussed with the Medical Monitor prior to rescreening. The participant must be re-consented/assented if approved for rescreening. In addition, all Screening assessments must be repeated with the exception of imaging, echocardiogram, and the ophthalmic assessment, which would only be repeated if the assessments were obtained > 45 days prior to the first dose of study treatment. There is no set limit to how many times a participant may be rescreened if the Investigator considers the rescreening medically and scientifically appropriate. Rescreened participants will be assigned a new participant number at the time of rescreening using interactive response technology (IRT).

6. Study Treatment

Study treatment for this study is defined as investigational product and intended to be administered to a study participant according to the study protocol. For this protocol, study treatment refers to capsules or dispersible tablets (pediatric formulation) of mirdametinib (PD-0325901).

6.1. Study Treatment Administered

- Participants utilizing the **capsule** dosage form of study treatment:
 - Participants will be instructed to swallow capsules whole and not to open or chew them prior to swallowing.
 - o No capsule should be ingested if it is broken, cracked, or otherwise not intact.
- Participants utilizing the **dispersible tablet** (pediatric formulation) dosage form of study treatment:
 - Additional dosage preparation instructions must be provided to the participant and/or primary caregiver.
 - Participants will be instructed to disperse the tablet(s) in water in a provided oral dosing syringe immediately prior to administration. Tablet(s) should never be crushed, chewed, or swallowed whole.
- Participants should be encouraged to take their dose approximately every 12 hours and can be taken without regard to food.
- Delivery of any dosage form of mirdametinib (PD-0325901) via nasogastric tube or gastrostomy tube is not allowed.
- During the Treatment Phase, participants will be instructed to record daily administration of study treatment dose in a home electronic patient reported outcome (ePRO) device, which will be provided by the Sponsor. Missed doses will also be recorded in the home ePRO device. For participants < 12 years of age, the primary caregiver will be asked to complete the electronic dosing diary.
- If a participant misses a scheduled dose of study treatment, and it is within 6 hours of the scheduled dose, the participant should immediately administer the missed dose and resume study treatment in accordance with the normal administration schedule. If more than 6 hours has elapsed since the time of scheduled administration, the participant will **not** be instructed to administer the missed dose and to resume study treatment as prescribed.
- Participants should not take 2 doses together to "make-up" for a missed dose.

- If a participant vomits any time after taking a dose, then they must be instructed not to take another dose to "make up" for vomiting, but rather, to resume subsequent doses as prescribed.
- If a participant inadvertently takes 1 extra dose, then the participant should not take the next scheduled dose of study treatment.
- If applicable, instructions related to dosing should be provided to parent(s)/legal guardians as well as study participants.

Table 3 Study Treatment Administration

ARM Name	Treatment					
Treatment Name	Mirdametinib (PD-0325901)					
Туре	Drug					
Dose Formulation	Capsule	Dispersible tablets				
Unit Dose Strength(s)	1 mg and 2 mg 0.5 mg and 1 mg					
Drug Product Components	mirdametinib, microcrystalline cellulose, croscarmellose sodium, magnesium stearate, hard gelatin capsule shell mirdametinib, microcrysta cellulose, croscarmellose sodium, magnesium stearate, sucralose, grape flavor					
Dosage Level(s)	2 mg/m ² (maximum single dose of 4 mg, BID)					
Route of Administration	Oral					
Sourcing	Sponsor will provide Sites with study treatment for individual participant distribution. Oral syringes will also be provided for participants utilizing the dispersible tablet formulation.					
Packaging and Labeling	Study treatment will be provided in 75 count bottles. Each bottle will be labeled as required per country requirement.					
Former Names	PD-0325901-00, PD-0325901-0	0000, PF-00192513-00				

6.1.1. Study Treatment Dosing and Administration

Once the informed consent/assent process (Section 10.1.3) has been conducted and all entry criteria have been met, study treatment will be assigned and dispensed using the IRT. The default formulation of study treatment will be the capsule. If a participant requires the use of the dispersible tablet (pediatric formulation) dosage form, this must be specifically requested in the IRT. The first dose of study treatment will then be administered orally at the Site followed by a \geq 2-hour observation period.

Throughout the Treatment Phase, participants will self-administer study treatment BID (twice daily [approximately every 12 hours without regard to food]), utilizing an intermittent (3 weeks on/1 week off) dosing schedule in 28-day Cycles. If the participant is receiving the dispersible tablet (pediatric formulation) dosage form of study treatment, dosing instructions must be provided to detail dose preparation and administration utilizing provided oral dosing syringes.

Participants will be instructed to **not** take their planned morning dose prior to each study visit during the Treatment Phase. Instead, the morning dose will be taken following the pre-dose PK blood draw. To accommodate site scheduling, modifications to holding the morning dose for the purposes of PK sample collection may be made on a case-by-case basis with prior approval from the Sponsor.

Study treatment (and oral syringes if the dispersible tablets [pediatric formulation] are utilized) will be dispensed to participants every 2 Cycles during scheduled study visits in the Treatment Phase and every 4 Cycles in the LTFU Phase as described in the SoA (Section 1.3, Section 1.4) or unscheduled visits if study treatment is damaged/lost or dose modification (Section 6.6) is necessary.

Participants enrolled in the LTFU Phase of the study will continue taking the last dose assigned in the Treatment Phase (approximately 2 mg/m² BID [maximum dose of 4mg BID]) of PD-0325901 (mirdametinib; open-label study treatment), on an intermittent (3 weeks on/1 week off) dosing schedule in 28-day cycles unless a dose modification is required (e.g., BSA change).

6.1.2. Study Treatment Errors

Study treatment errors may result in this study from the administration or consumption of the study treatment by the wrong participant or at the wrong dosage strength. Such study treatment errors occurring to a study participant are to be captured in the electronic case report form (eCRF) when appropriate. Missed doses are not considered dosing errors. In the event of a dosing error, the Medical Monitor should be notified immediately.

Study treatment errors are reportable irrespective of the presence of an associated AE/SAE, including errors involving participant exposure to the product.

If the study treatment error is accompanied by an AE (as determined by the Investigator), the study treatment error (if applicable), and any AE(s), must be captured on an AE eCRF page.

6.2. Preparation/Handling/Storage/Accountability

Only participants enrolled in the study, who meet study entry criteria (Sections 5.1 and 5.2) may receive study treatment, as assigned by the IRT. Only authorized Site personnel may supply or administer study treatment (PD-0325901, mirdametinib). Only in extenuating circumstances and with written permission from the Sponsor, direct to participant shipment of study treatment may be accommodated via site request.

Preparation:

• Study treatment does not require special preparation by Site personnel prior to dispensing to participants. If the dispersible tablet (pediatric formulation) is being utilized, oral dosing syringes will be supplied with study treatment for participant/primary caregiver preparation and administration.

- Study treatment will be supplied as hard gelatin capsules (1- and 2-mg) or rapidly dispersible tablets (0.5- and 1-mg) for oral administration.
- Study treatment will be packaged in high-density polyethylene bottles.
- Participants will be instructed to keep their study treatment in the original bottles provided by the Sponsor and not transfer it to any secondary containers.

Handling:

- Study treatment must be handled by authorized/delegated Site personnel only.
- No special handling of study treatment is required.

Storage:

- Capsules must be stored at 15°C to 30°C (59°F to 86°F). Dispersible Tablets must be stored at 15°C to 25°C (59°F to 77°F).
- The Investigator or designee must confirm appropriate temperature conditions have been maintained during transit for all study treatment received and any discrepancies are reported and resolved before use of the study treatment.
- All study treatment must be stored in a secure, environmentally controlled, and monitored (manual or automated) area in accordance with the labeled storage conditions with access limited to the investigator and authorized Site staff.

Accountability:

- The Investigator, institution, or the head of the medical institution (where applicable) is responsible for study treatment accountability, reconciliation, and record maintenance (i.e., receipt, reconciliation, and final disposition records).
- Participants will be instructed not to dispose of any study treatment bottles, and to bring all bottles (used and unused) back to the Site at every visit.
- Accountability will be performed by Site personnel at each dispensing visit as described in the SoA (Section 1.3, Section 1.4), and participants will be re-educated about the importance of following the prescribed dosing regimen (if compliance is low).
- Returned study treatment will not be re-dispensed to the participants.
- Further guidance and information for the final disposition of unused study treatments are provided in the pharmacy manual.

6.3. Measures to Minimize Bias: Randomization and Blinding

This study is an open-label, single arm/intervention study; potential bias will be reduced by the utilization of an independent, blinded, central radiologic review for the primary endpoint adjudication and analysis.

Study treatment blinding and randomization are not applicable in this study.

6.4. Study Treatment Compliance

Participant compliance with study treatment will be assessed at each visit where study treatment is dispensed. Compliance will be assessed by counting returned capsules/dispersible tablets in addition to reviewing the dosing diary entries from the home ePRO device used in the Treatment Phase (participants will be trained on the home ePRO device at the Screening visit). At each study visit, any discrepancies or deviations will be discussed with the participant and will be recorded in the source documentation. The number of capsules/dispersible tablets dispensed, and the number of capsules/dispersible tablets returned will be recorded in the eCRF, as well as any deviations. In the case of an overdose, refer to Section 8.4 for instructions.

6.5. Concomitant Therapy

6.5.1. Prior/Concomitant Medications and/or Procedures

Any medication or vaccine (including over-the-counter or prescription medicines, vitamins, and/or herbal supplements) that the participant is receiving at the time of signing informed consent/assent or receives during the study must be recorded along with:

- Reason for use
- Dates of administration including start and end dates
- Dosage information including dose and frequency

The Medical Monitor should be contacted if there are any questions regarding concomitant or prior therapy. Refer to Section 10.10.3 for the Medical Monitor contact details.

6.5.2. Prohibited or Restricted Concomitant Medications/Treatments

- Prior use of mirdametinib (PD-0325901) or any other MEK 1/2 inhibitor is prohibited.
- Alternative therapy for the treatment of PNs (e.g., farnesyltransferase inhibitors, kinase inhibitors, etc.) within 45 days (or 5.5 half-lives, whichever is longer) of first dose of study treatment and throughout the Treatment Phase or LTFU Phase is prohibited.
- Medical treatment (e.g., chemotherapy, biologic therapy, radiation therapy) directed towards any NF1-related tumor such as optic pathway glioma is prohibited throughout the Treatment Phase or LTFU Phase.
- The use of chronic systemic, inhaled, or ocular glucocorticoid therapy is prohibited within the 14 days prior to first dose of study treatment and throughout the Treatment Phase or LTFU Phase with the following exceptions:
 - Physiologic or stress doses of steroids, when indicated in participants with endocrine deficiencies
 - Glucocorticosteroids given as the premedication for blood product transfusions

- Glucocorticosteroids given as the pulse treatment for an acute allergic reaction or bronchospasm
- Oral or intravenous glucocorticosteroids for up to 6 consecutive days, when indicated for the management of an adverse event only after consultation with the Medical Monitor and/or ophthalmologist
- Topical steroids for dermatological purposes are permitted at the discretion of the Investigator

6.5.3. Supportive Care

Refer to Section 10.12.

6.6. Dose Modification

Every effort should be made to administer study treatment at 2 mg/m² BID; however, in the event of significant toxicity, dosing must be interrupted and/or dose reduced as described in Table 4 and Table 5.

Interruption of study treatment should continue until the toxicity is resolved to \leq Grade 1 or Baseline. An interruption of study treatment for more than 14 days due to any toxicity may require permanent discontinuation. After 14 days of interruption, study treatment may be resumed only after discussion with the Medical Monitor and approval by the Sponsor. Refer to Section 10.10.3 for the Medical Monitor contact details.

After interruption, study treatment may be resumed at a reduced dose as described in Table 4 and Table 5. Should the same Grade toxicity recur at the reduced dose and the AE is considered related to the study treatment, the participant may be discontinued at the discretion of the Investigator, pursuant to discussion with the Medical Monitor and Sponsor. Following a dose reduction, an increase in the study treatment dose due to a BSA change is permitted at the discretion of the Investigator with approval from the Medical Monitor and Sponsor.

An unscheduled visit may be performed at any time during the study. Assessments to be performed at the visit will be determined by the Investigator.

Table 4 Criteria For Dose Modification For Study Drug Related Adverse Events

RELATED ADVERSE EVENTS	INTERVENTION
OCULAR/VISUAL	
Any Grade ≤ 2 event.	Continue dosing and perform ophthalmologic exams every 2 to 4 weeks until resolution to Grade ≤ 1 or baseline.
Any Grade ≥ 3 event except RVO.	Interrupt dosing; if resolution to Grade ≤ 1 or baseline occurs within 14 days, re-start study treatment at the next lower dose following Table 5. Consider ophthalmologic exams every 2 to 4 weeks.
Grade ≥ 3 retinal vein occlusion (RVO)	Permanently discontinue study treatment
NEUROLOGICAL	
Grade ≤ 2 events such as hallucination, confusion or delirium lasting more than 24 hours AND after ruling out other possible causes.	Interrupt dosing; if resolution to Grade ≤ 1 or baseline occurs within 14 days, re-start study treatment at the next lower dose following Table 5.
Any Grade ≥ 3 event.	Withhold dose and discuss with the Medical Monitor. Consider permanent discontinuation after re-evaluating the benefit risk of ongoing study drug treatment
MUSCULOSKELETAL	
Grade \geq 3 muscle weakness (symptomatic and interfering with ADL).	Interrupt dosing; if resolution to Grade ≤ 1 or baseline occurs within 14 days, re-start study treatment at the next lower dose following Table 5.
DERMATOLOGICAL	
Grade ≥ 3 acneiform rash.	Interrupt dosing; if resolution to Grade ≤ 1 or baseline occurs within 14 days, restart study treatment at the next lower dose following Table 5.
CARDIAC	
Asymptomatic, absolute decrease in left ventricular ejection fraction (LVEF) of \leq 10% from baseline and is below institutional lower limit of normal (LLN).	Interrupt dosing; if LVEF value improves to above the institutional LLN or baseline, resume at the same dose, if supported by the investigator's assessment of the benefit-risk ratio.
	If LVEF does not improve to above the institutional LLN or baseline within 14 days, permanently discontinue study treatment.

Asymptomatic, absolute reduction in LVEF of $> 10\%$ to $\le 19\%$ from baseline and is below institutional lower limit of normal (LLN).	Interrupt dosing; if LVEF value improves to above the institutional LLN or baseline within 14 days, resume at the next lower dose level following Table 5. If LVEF does not improve to above the institutional LLN or baseline within 14 days, permanently discontinue study treatment.
Symptomatic congestive heart failure. Absolute decrease in LVEF of greater than 20% from baseline.	Permanently discontinue study treatment.
LIVER (Refer to Section 7.1.1)	
OTHER	
Grade \geq 3 hematologic toxicities or clinically significant Grade 2 hematologic abnormalities, that do not resolve within 72 hours after initiation of medical management.	Interrupt dosing; if resolution to Grade ≤ 1 occurs within 14 days, restart study treatment at the next lower dose following Table 5.
Grade ≥ 3 nonhematologic toxicity that is not controlled by optimal supportive medication.	Interrupt dosing; if resolution to Grade ≤ 1 or baseline occurs within 14 days, restart study treatment at the next lower dose following Table 5.
Other Grade 2 toxicity that is subjectively intolerable (except alopecia) and not controlled by optimal supportive medication.	Interrupt dosing; if resolution to Grade ≤ 1 or baseline occurs within 14 days, re-start study treatment at the same dose.
Recurrent subjectively intolerable toxicity (at least a week interruption on 2 occasions) that is not controlled by optimal supportive medication.	Interrupt dosing; if resolution to Grade ≤ 1 or baseline occurs within 14 days, restart study treatment at the next lower dose using Table 5. If toxicity is still intolerable, permanently discontinue study treatment (unless otherwise discussed with the Medical Monitor or Sponsor).

ADL=activities of daily living; CHF=congestive heart failure; LLN=lower limit of normal; LVEF=left ventricular ejection fraction

In the event a dose reduction is required, the study treatment total daily dose will be reduced as follows in Table 5:

Table 5 Dose Reduction

Capsule dosage form

Dose at the time of the event	Reduced dose
1 mg BID	1 mg AM
2 mg BID	2 mg AM; 1 mg PM
3 mg BID	2 mg BID
4 mg BID	3 mg BID

BID = twice daily; mg= milligrams

Capsule dosage form Dose Modification Nomogram

BSA (m ²)	0.4 to 0.69	0.7 to 1.04	1.05 to 1.49	≥1.5	
Modified Dose	1 mg AM	2 mg AM, 1 mg PM	2 mg BID	3 mg BID	

BID = twice daily; BSA = body surface area; mg = milligrams

All study dosing will be administered on a 3 weeks on/1 week off intermittent schedule

Dispersible tablet dosage form (pediatric formulation)

Dose at the time of the event	Reduced dose				
1 mg BID	1 mg AM; 0.5 mg PM				
1.5 mg BID	1 mg BID				
2 mg BID	1.5 mg BID				
2.5 mg BID	2 mg AM; 1.5 mg PM				
3 mg BID	2.5 mg AM; 2 mg PM				
3.5 mg BID	2.5 mg BID				
4 mg BID	3 mg AM; 2.5 mg PM				

BID = twice daily; mg= milligrams

Dispersible tablet dosage form (pediatric formulation) Dose Modification Nomogram

BSA (m ²)	0.4 to 0.59	0.6 to 0.79	0.8 to 0.99	1 to 1.39	1.4 to 1.59	1.6 to 1.69	≥ 1.7
Modified Dose	1 mg AM, 0.5 mg PM	1 mg BID	1.5 mg BID	2 mg AM, 1.5 mg PM	2.5 mg AM, 2 mg PM	2.5 mg BID	3 mg AM, 2.5 mg PM

BID = twice daily; BSA = body surface area; mg = milligrams

All study dosing will be administered on a 3 weeks on/1 week off intermittent schedule

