If an abscess develops, surgical treatment with incision and drainage with or without debridement should be done. Any infectious organisms identified should be treated accordingly. If the participant has diabetes or is immune compromised, oral antibiotics ensuring coverage for staphylococcal aureus (see above) should be started prior to a culture and sensitivity report. Once culture report is obtained, the antibiotic therapy should be adjusted as appropriate.

Visual adverse events:

All participants will have a detailed ophthalmologic evaluation at Screening. In participants who develop visual symptoms, a repeat ophthalmologic evaluation will be performed to include: best corrected visual acuity, intraocular pressure, slit lamp fundoscopy (photograph if abnormal).

If a diagnosis of retinal pigment epithelial detachment or central serous retinopathy is made, treatment with PD-0325901 will be held and repeat ophthalmologic evaluations will be performed until resolution. Treatment may be restarted after complete resolution of symptoms to baseline.

If a diagnosis of retinal vein occlusion (RVO) is made, PD-0325901 will be discontinued permanently.

Gastrointestinal adverse events:

Diarrhea: Non-infectious diarrhea should be treated with loperamide. Additional agents may be used concurrently if loperamide is not adequate to control diarrhea as a single agent. In addition, the following dietary advice should be considered: BRAT diet (bananas, rice, apple sauce, toast, plain pasta), readily digestible food, avoidance of lactose-containing products and fried, fatty or spicy foods, increased fluid intake (8-10 glasses of clear fluids/day (including water, clear broth, fluids containing salt and sugar). Participants should be encouraged to seek advice early from their physician or study nurse if they have persistent diarrhea, diarrhea complicated by vomiting, or inability to take oral liquids.

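### For drug-related retinal vein occlusion of Grade 2 or lower, Table 4 continues dosing while Appendix 12 stops it permanently, and no text says which governs; a weaker conflict affects two symptomatic retinal diagnoses

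*Protocol*

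**What the plan says.** Table 4 is titled "Criteria For Dose Modification For Study Drug Related Adverse Events", so it covers related events only. Section 6.6 makes it binding for significant toxicity: "dosing must be interrupted and/or dose reduced as described in Table 4 and Table 5". It has three ocular rows.

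- The first row tells sites: "Continue dosing and perform ophthalmologic exams every 2 to 4 weeks until resolution to Grade ≤ 1 or baseline". It applies to every event of Grade 2 or lower and names no exception.
- The second row, "Any Grade ≥ 3 event except RVO", has the site interrupt, and restart at the next lower dose if the event returns to Grade 1 or lower, or to baseline, within 14 days.
- "Grade ≥ 3 retinal vein occlusion (RVO"): permanent discontinuation.

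Appendix 12, under visual adverse events, goes by diagnosis and gives no grades.

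- RVO: "If a diagnosis of retinal vein occlusion (RVO) is made, PD-0325901 will be discontinued permanently".
- The other two diagnoses: "If a diagnosis of retinal pigment epithelial detachment or central serous retinopathy is made, treatment with PD-0325901 will be held". Eye evaluations are repeated until resolution, and restart requires symptoms to have resolved completely to baseline.
- These instructions follow a lead-in about symptoms: "In participants who develop visual symptoms, a repeat ophthalmologic evaluation will be performed".

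Section 6.5.3 points to Appendix 12 but gives no order of precedence.

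**The concern.** A site with a related Grade 2 RVO finds one instruction to keep dosing and another to stop for good. It cannot follow both. Section 6.6 sends investigators to Tables 4 and 5, so the table is the place a site would normally look. A site that follows it literally keeps dosing through an eye event for which the same protocol requires a permanent stop.

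For symptomatic retinal pigment epithelial detachment or central serous retinopathy the disagreement is between continuing and holding. After a Grade 3 or higher event it concerns how complete the recovery must be before restart. What is at stake is participant safety and consistent handling across sites, not the efficacy inference.

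**Working it through.** The plan gives no figure to reproduce, so the check sets the two texts side by side.

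| Related event | Table 4 (Section 6.6) | Appendix 12 (Section 10.12) | Agree? |
|---|---|---|---|
| RVO, Grade ≤ 2 | Continue, with exams | Stop permanently | No |
| RVO, Grade ≥ 3 | Stop permanently | Stop permanently | Yes |
| Symptomatic pigment epithelial detachment or central serous retinopathy, Grade ≤ 2 | Continue, with exams | Hold | No |
| The same two diagnoses, symptomatic, Grade ≥ 3 | Interrupt; restart at Grade ≤ 1 or baseline, lower dose | Hold; restart after complete resolution of symptoms to baseline | On interrupting, yes; on restart, no |

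**Does the Grade ≤ 2 row include RVO?** As written, yes. The next row excepts RVO and the first does not, and the separate RVO row begins at Grade 3.

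**Does any other text set precedence?**

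- Section 6.6 names Tables 4 and 5 and does not mention Appendix 12.
- Section 6.5.3 is a bare pointer.
- Section 7.1 lists RVO, ungraded, among possible reasons for stopping, tied to the Investigator's judgement. It permits stopping but does not settle the conflict.
- Section 10.1.7 makes one RVO, ungraded, a listed reason to suspend or terminate enrollment, while the same bullet sets a Grade 3 threshold for optic neuropathy, detachment and retinopathy. It does not address the affected participant's dosing. Read with Table 4, a Grade 2 RVO could halt enrollment while that participant keeps dosing.
- The introduction to Section 8 sends immediate safety concerns to the Sponsor or Medical Monitor for a decision on continuing. Section 8.3.1 requires 24-hour reporting of listed eye events, RVO included, from Grade 2. Both are decision routes, not dosing rules.
- SAP Section 4.3.7 only refers back to protocol Section 6.6.

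**Size per affected participant, as an illustration.** The count covers a Grade 2 event, from diagnosis to the next exam Table 4 requires, and assumes nobody intervenes. Inputs are twice-daily dosing, 21 days on and 7 off (Synopsis), and an exam interval of 2 to 4 weeks (Table 4). For a window of L days, from 7 to 28, dosing days range from L − 7 to the smaller of L and 21.

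- L = 14: 7 to 14 dosing days, × 2 = 14 to 28 doses.
- L = 28: 21 dosing days, × 2 = 42 doses.
- At the 4 mg maximum: 14 × 4 = 56 mg to 42 × 4 = 168 mg.
- At 1 mg twice daily, the lowest starting dose in Table 2: 14 to 42 mg.

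Appendix 12 gives 0 doses after an RVO diagnosis and 0 during a hold. For a Grade 1 event the end-point of Table 4's exams is already met, so no interval applies.

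**The case against.** The best reply is that nobody would in fact be dosed through an RVO. Appendix 12 is specific to the diagnosis, and Table 4's first row is a catch-all. RVO appears without a grade in Section 7.1, Section 10.1.7 and Appendix 12, so stopping is the natural reading. An ophthalmologist does the exams, evidence of disease leads to a full evaluation (Section 8.2.7), Exclusion 12 screens out retinal risk factors, and the reporting and escalation routes above apply. Dosing silently through a Grade 2 RVO would need several safeguards to fail.

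Most of this stands, and it lowers the practical risk. A reader might infer that the protocol leaves such a participant dosing unnoticed for weeks; the documents do not support that, and the dose counts are not an estimate of harm.

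The reply does not remove the contradiction. Table 4 is also specific about RVO, since it excepts RVO in one row and gives it a graded row of its own. That limit may even have been intended. A Medical Monitor who receives the report still has two opposite instructions.

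The objection also rightly limits the reach. Appendix 12's lead-in and restart condition speak of symptoms, so a conflict for asymptomatic detachment or serous retinopathy is arguable, not shown. The documents do not say how these diagnoses are graded, so whether a Grade 1 RVO can occur is not shown either.

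**Conclusion.** The conflict is real for study-drug-related RVO of Grade 2 or lower. It is real but weaker for symptomatic retinal pigment epithelial detachment and central serous retinopathy, on continuing versus holding at Grade 2 or lower and on the restart condition at Grade 3 or higher. No text settles precedence, although the ungraded mentions of RVO favour stopping.

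The documents give no incidence at this dose, and none is assumed. Section 2.3 says the listed events, RVO among them, arose mainly at 10 mg twice daily or more; the maximum here is 4 mg twice daily. RVO is therefore likely uncommon. That section does not mention the other two diagnoses.

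A reader might infer that the flaw must be fixed before the trial can be relied on, or that it extends to unrelated events. Neither follows: Table 4 covers related events only, and no power, error-rate or endpoint figure is touched. This is a safety-text inconsistency that should be fixed. The conclusion rests on reading Table 4's first row as written and on Grade 2 RVO being possible, which fits the Grade 2 reporting threshold for eye disorders in Table 10.

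**What to change.** 1. In Table 4, change the RVO row to *RVO, any grade: permanently discontinue*, and except RVO from the Grade ≤ 2 row.
2. Except symptomatic retinal pigment epithelial detachment and central serous retinopathy from both general ocular rows. Add one row: *symptomatic, any grade: hold; repeat eye evaluation until resolved; restart only once symptoms have resolved completely to baseline, subject to the 14-day rule in Section 6.6*.
3. Cross-reference Table 4 and Appendix 12, and state that the stricter instruction governs.

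The sponsor should decide how asymptomatic findings are handled and what dose is used at restart. Adding grade limits to Appendix 12 would also remove the contradiction, but the ungraded RVO wording in Sections 7.1 and 10.1.7 makes the stricter direction the better fit.

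The cost is a text-only protocol amendment. It changes a stopping rule, so it needs IRB/IEC approval under Section 10.1.1. It adds no visits or procedures.
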